9.0 Vulnerable Populations

9.1 Vulnerable Populations:

Population / Group	Identify whether any of the following populations will be targeted, included (not necessarily targeted) or excluded from participation in the study.
Children	Targeted Population
Pregnant women/fetuses/neonates	Excluded from Participation
Prisoners	Excluded from Participation
Adults lacking capacity to consent and/or adults with diminished capacity to consent, including, but not limited to, those with acute medical conditions, psychiatric disorders, neurologic disorders, developmental disorders, and behavioral disorders	Excluded from Participation
Non-English speakers	Excluded from Participation
Those unable to read (illiterate)	Included/Allowed to Participate
Employees of the researcher	Excluded from Participation
Students of the researcher	Excluded from Participation
Undervalued or disenfranchised social group	Included/Allowed to Participate

MEDICAL PROTOCOL (HRP-590)

PROTOCOL TITLE: Piloting a Family-Based Intervention of Time-Restricted Eating to Treat Obesity

VERSION DATE: 07Sep2022

Active members of the military (service members), DoD personnel (including civilian employees)	Excluded from Participation
Individual or group that is approached for participation in research during a stressful situation such as emergency room setting, childbirth (labor), etc.	Excluded from Participation
Individual or group that is disadvantaged in the distribution of social goods and services such as income, housing, or healthcare.	Included/Allowed to Participate
Individual or group with a serious health condition for which there are no satisfactory standard treatments.	Included/Allowed to Participate
Individual or group with a fear of negative consequences for not participating in the research (e.g. institutionalization, deportation, disclosure of stigmatizing behavior).	Included/Allowed to Participate
Any other circumstance/dynamic that could increase vulnerability to coercion or exploitation that might influence consent to research or decision to continue in research.	Included/Allowed to Participate

9.2 Additional Safeguards:

Children will be part of the targeted enrollment for this study. As the children enrolled will be between the ages of 3 and 9, we will only ask for the child to assent if they are aged 8-9; children aged 3-7 will be exempt from the assent process. The parent who also enrolls (to complete the dyad) will consent for study participation and will also sign the parental consent indicating that their child can participate in the study.

10.0 Local Number of Participants

10.1 Local Number of Participants to be Consented: A total of 20 parent/child dyads (40 total individuals) will be asked to participate in the study. 10 parent/child

MEDICAL PROTOCOL (HRP-590)

PROTOCOL TITLE: Piloting a Family-Based Intervention of Time-Restricted Eating to Treat Obesity

VERSION DATE: 07Sep2022

dyads will be randomized to standard care and 10 parent/child dyads will be randomized to time-restricted eating.

11.0 Local Recruitment Methods

11.1 Identification of Potential Participants: Recruitment will be achieved by a number of methods that have been effective in the Center for Pediatric Obesity Medicine (CPOM) as well as in the Department of Medicine in the past. These include mailing letters to potentially eligible participants based on an initial screening of eligibility in the electronic health record, as well as clinical recruitment efforts by members of the investigation team and other physicians within CPOM and the Medical School. Notably, within MHealth Fairview Clinics, there are over 14,000 children aged 3-9 with obesity who are potentially eligible participants.

Retention of patients with obesity can be particularly challenging; thus, we have established robust methods over the years that allow successful retention of youth and families. Our history of successfully conducting clinical trials of obesity treatments provides evidence that we can realistically retain the required number of participants.¹⁷ We will maximize our ability to do this by expressing our gratitude for their time and effort, providing the highest level of customer service possible, establishing rapport and trust with the families, and facilitating regular communication among the investigators. Additionally, we will monitor the recruitment and retention rates monthly and will adjust our retention and recruitment strategies if indicated.

11.2 Recruitment Materials: Letters and flyers will be developed for this project and sent to the IRB for approval before implementation.

11.3 Payment: Families will be appropriately compensated for their time. Each family will receive \$35 per in-person visit and \$15 for each virtual session. The total compensation will be \$175/family. They will also be allowed to keep the Bluetooth-enabled scale and the Bluetooth-enabled toothbrushes at the end of the study. Payments to the parent/child dyad will be made via Greenphire ClinCard.

12.0 Withdrawal of Participants

12.1 Withdrawal Circumstances: Individuals are free to withdraw from study participation at any time, they should just inform the study team.

12.2 Termination Procedures: Data that had been collected before the dyad elected to withdraw from the study will be kept in the participant file. No additional information will be collected from the dyad after they have indicated that they no longer want to participate in the study.

MEDICAL PROTOCOL (HRP-590)

PROTOCOL TITLE: Piloting a Family-Based Intervention of Time-Restricted Eating to Treat Obesity

VERSION DATE: 07Sep2022

12.3

13.0 Risks to Participants

13.1 Foreseeable Risks: Risks for this study are minimal and include discomfort with recalling and reviewing meals, tiring of filling out daily REDCap inquiries, and potential frustrations (for the TRE group) with trying to brush their teeth in the evening within 30 minutes of finishing their evening meal. There could be discomfort or dissatisfaction with limiting food intake to the eating window hours and/or with limiting caloric intake per standard of care recommendations. There is also a risk of breach of confidentiality.

13.2 Reproduction Risks: Not applicable.

13.3 Risks to Others: Not applicable.

14.0 Potential Benefits to Participants

14.1 Potential Benefits: Due to the interventions and self-monitoring, it is possible that participating in this study will lead to weight loss, which is desirable since we are enrolling participants with obesity. Families may also have increased awareness about the food that is being consumed and how portion control or limiting the times during the day that food is ingested can be helpful in weight loss. It is hoped that the dietitian intervention might help parents find strategies to encourage healthy eating within the home.

15.0 Statistical Considerations

Analysis Plan: We will summarize feasibility and adherence measures (recruitment and retention rate, proportion of days with documented eating window, eating window length) using sample proportions, means (standard deviations), and medians (interquartile ranges). Proportion of families completing the study (retention rate) will be compared between intervention groups using Fisher's exact tests. Agreement between toothbrush reported eating window and survey reported eating window will be evaluated using mixed effects models¹⁶ (to account for repeated measures for each family) and Bland-Altman Plots.¹⁷

The primary outcome analysis will use a linear GEE model, with independence working correlation for family units, to compare change in BMI during the 12-week period (pre-post) between participants assigned to the TRE intervention compared to the standard of care. This model will allow for estimating the TRE effect for children and adults while accounting for the correlation between parent and child measures. If we do not detect a difference in TRE effect for children and adults ($p\text{-value} \geq 0.1$) the treatment assignment by child indicator interaction will be removed from the model. A similar approach will be used to compare changes in measures of diet quality (average caloric intake and HEI), eating and feeding behaviors, appetite, and quality of life measures between groups. Generalized linear mixed effects models will be used to evaluate

MEDICAL PROTOCOL (HRP-590)

PROTOCOL TITLE: Piloting a Family-Based Intervention of Time-Restricted Eating to Treat Obesity

VERSION DATE: 07Sep2022

differences in weight trajectory between intervention groups. We will evaluate the correlation between parent and child change in BMI during the study using Pearson's correlation coefficient, or Spearman's correlation coefficient (if data visualizations indicate a non-linear trend). Total intervention time (sum of session time across the study) will be compared between groups using t-tests (or Wilcoxon rank sum tests if measures are highly skewed).

We will check data distributions before conducting statistical tests and will transform the data if the normality assumption is not met. Logistic regression models will be used in place of linear regression models for binary data, as appropriate. Analyses will be performed in R or SAS (Version 9.4, SAS Institute Inc., Cary, NC)

Sample Size: Since the primary purpose of this pilot study is to collect preliminary data (specifically feasibility and variability measures) to inform study design for a fully powered clinical trial, this pilot study is powered to detect large differences in BMI change between groups. With n=20 per group (10 child-parent pairs), correlation between child-parent pairs ranging from 0.1 to 0.8, and an alpha= 0.05 significance level, we will have 80% power to detect a difference in BMI change (pre-post) between treatment groups of 0.96 to 1.25 standard deviations (Cohen's d of 0.96 to 1.25, a large effect size).

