3.0 Study Endpoints/Events/Outcomes

- 3.1 Primary Endpoint/Event/Outcome: Evaluate feasibility and acceptability of implementing TRE in families by quantifying recruitment, adherence and intervention burden. We anticipate that we will recruit ~3 families per month for a total of 10 families in each intervention group (N=20), with a retention rate of 70-80% across both groups.

MEDICAL PROTOCOL (HRP-590)

PROTOCOL TITLE: Piloting a Family-Based Intervention of Time-Restricted Eating to Treat Obesity

VERSION DATE: 07Sep2022

- In the TRE group, there will be close agreement between tooth brushing times (recorded with Bluetooth-enabled toothbrush) and self-reported eating window.
- Family-based TRE will result in less intervention burden than intentional caloric restriction, as documented by less staff time administering the intervention.

[figure not shown]
3.2 Secondary Endpoint(s)/Event(s)/Outcome(s):

- Compare weight/BMI change between the TRE group and the SOC group. We hypothesize that the weight/BMI outcomes between the two groups will be comparable.
- Assess relationship between child and adult weight/BMI outcomes with TRE. We hypothesize that parent and child weight/BMI change will be positively correlated.

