In the TRE group, study staff will instruct the family unit on limiting the eating window to 10-12 hours per day, during which they can eat ad libitum. Notably, in the TRE group, participants (children and adults) will be instructed to brush their teeth with a Bluetooth-enabled toothbrush in the morning and specifically within $\frac{1}{2}$ hour after their evening meal. This will serve as a cue to stop evening eating, and information from the Bluetooth-enabled toothbrush will be accessed by study staff to approximate the eating window. The adult from each family unit will receive a periodic REDCap-administered emails to indicate the timing of the first meal of the day and the last meal of the day for the parent and child, which will also serve as an estimate of the eating window.

The standard of care control group will receive dietary instruction that is based on a 1200-1500 calorie diet, as is typical of family-based interventions. Families will be encouraged to follow appropriate portion sizes; increase vegetable, fruit and lean protein consumption; as well as decrease consumption of energy-dense but low-quality items (e.g., sugar sweetened beverages). Families in this group will also receive a Bluetooth-enabled toothbrush and periodic REDCap surveys but will not be instructed on when to brush teeth or to shorten their eating window.

In both intervention groups, the child and adult participant will weigh themselves on a consistently weekly basis, using a Bluetooth-enabled scale. This is a common aspect of behavioral weight loss interventions (i.e., self-monitoring) and will serve as ongoing data collection (see outcomes below). Additionally, treatment will be

MEDICAL PROTOCOL (HRP-590)

PROTOCOL TITLE: Piloting a Family-Based Intervention of Time-Restricted Eating to Treat Obesity

VERSION DATE: 07Sep2022

primarily delivered to the adult participant, as prior research indicates adult-only sessions are as effective as joint sessions for younger children.^{7,9,10} That is, parents and children will attend two in-person sessions: baseline and 12 weeks. Only parents will attend virtual sessions. Sessions occur on a weekly basis for the first 4 weeks and every other week for the final 8 weeks (see Schedule of Events).

4.2 Drug/Device Handling: Not applicable.

4.3 Biosafety: Not applicable.

4.4 Stem Cells: Not applicable.

4.5 Fetal Tissue: Not applicable.

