8.2 Exclusion Criteria

- Concurrent participation in another weight loss study
- Taking any medications for weight loss
- Pregnancy or anticipation of pregnancy in next 6 months (for the parent)
- 3+ on Eating Disorder Survey (see attached)
- Must be on a stable dose of any weight-altering medications

8.3 Prescreening/Consent: Individuals who appear to meet the study criteria based on a pre-screening telephone call will be asked to participate in a virtual (video) visit. At that visit, consent will be discussed and obtained, height and weight will be self-reported by parent for both parent and child, so that estimated BMI can be calculated, and inclusion/exclusion criteria will be reviewed. Individuals who meet the BMI requirement and the inclusion/exclusion criteria will enroll in the study.

Following consent and prior to the Baseline/Week 0 session, parents will be

MEDICAL PROTOCOL (HRP-590)

PROTOCOL TITLE: Piloting a Family-Based Intervention of Time-Restricted Eating to Treat Obesity

VERSION DATE: 07Sep2022

contacted by the University of Minnesota Nutrition Coordinating Center (NCC) staff and will be asked to provide three 24-hour dietary recalls for themselves and for their child (for a total of six). NCC staff will be blinded to participant intervention assignment. Using this 24-hour dietary recall data, we will calculate the daily average caloric intake and healthy eating index, as well as the eating window.

Baseline/Week 0: Individuals will be asked to come to the Delaware Clinical Research Unit (DCRU). At that visit, height and weight will be measured so that BMI can be calculated. Individuals who no longer meet inclusion/exclusion criteria will be excluded (e.g., outside BMI range based on in-person measurement compared to self-reported). Participants who meet the inclusion/exclusion criteria will be randomized to their intervention group. Participants will be provided with a Bluetooth-enabled scale and instructed to weigh themselves once per week. Participants will also be provided with Bluetooth-enabled toothbrushes. Participants randomized to the TRE treatment will be asked to brush their teeth twice daily and to brush their teeth within 30 minutes after the evening meal to note that they have ceased eating until the next day.

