- I will use an external hard drive or USB drive ("flash" or "thumb" drives) not previously listed
- I will use a mobile device such as a tablet or smartphone not previously listed

16.8 Consultants. Vendors. Third Parties. Individuals participating in the study will download apps for the Bluetooth scale and the Bluetooth toothbrushes that will track their weights and toothbrushing times. The app for the scale will allow the user to share their data and participants will be asked to email the study team with their results (this can be sent in a csv format to the study team). The app for the toothbrush does not allow for sharing so individuals can screenshot their data and send to the study team or simply show the study team their phone to review the data at their visits. Data that is transmitted to the study team from the participant (such as the csv file for the scale data) will be stored in Box. It is our understanding from meeting with the HIPCO office that participants are free to send data to us and only after it is received by us, does it need to be protected.

16.9 Links to identifiable data: Csv files that the participants send to us that contain their Bluetooth scale information will be stored in Box as it is HIPAA compliant.

16.10 Sharing of Data with Research Team Members. Data will be kept in REDCap and Box and only those individuals who are working on the study will have access to these items.

16.11 Storage of Documents: Paper documents will be kept in individual participant binders and will be kept in an office that is locked when not in use. Electronic records may be kept in Box and REDCap, which utilize two level authentication.

16.12 Disposal of Documents: We anticipate keeping data for at least six years. When data is ready to be destroyed, a company that specializes in the shredding of confidential documents will be utilized to destroy any paper files.

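### The toothbrush agreement analysis names no arm and compares whole eating windows, although its hypothesis is for TRE only and only TRE evening brushing is tied to eating

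*Combined protocol and SAP*

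**What the plan says.** **Hypothesis.** Section 3.1 lists this under the primary endpoint: "In the TRE group, there will be close agreement between tooth brushing times (recorded with Bluetooth-enabled toothbrush) and self-reported eating window". It is limited to TRE and gives no figure for how close the agreement should be.

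**Analysis.** Section 15 evaluates "Agreement between toothbrush reported eating window and survey reported eating window" with mixed effects models, "to account for repeated measures for each family", and Bland-Altman plots. The sentence names no arm, makes no separate comparison of start and end times, and does not distinguish parent from child within the family.

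**Brushing instructions.** Section 4.1 tells TRE participants to "brush their teeth with a Bluetooth-enabled toothbrush in the morning and specifically within" half an hour after the evening meal. Section 8.3 (Baseline/Week 0) gives the purpose: "to brush their teeth within 30 minutes after the evening meal to note that they have ceased eating until the next day". The morning brush is not linked to the first meal anywhere. SOC families receive the same toothbrush but "will not be instructed on when to brush teeth or to shorten their eating window".

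**Data.** Section 4.1 gives toothbrushes to everyone to help monitor the eating window. Under the Schedule of Events (Section 5.1), all families log first and last eating times separately, for parent and child, on 5 consecutive days in three periods.

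**The concern.** A window has two ends. In TRE the evening brush is designed to mark the end of eating. The morning brush is not designed to mark its start, and in SOC neither brush is designed to mark anything. The planned analysis differs from the hypothesis in two ways:

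- **Arm.** Because Section 15 is silent on arm, SOC brushing may enter an analysis meant for a TRE hypothesis.
- **Ends.** A whole-window comparison adds an unanchored morning time to an anchored evening time. Wide limits could come entirely from the morning. Narrow ones could hide an evening failure offset by a morning error.

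This is one of two bulleted hypotheses under the primary endpoint, and the pilot is meant to inform a larger trial. The team will want to know whether evening brushing is a usable marker of the end of eating, and a whole-window summary alone does not answer that.

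**Working it through.** The plan gives no margin, precision or sample size for the agreement analysis, so it has no figure to reproduce. The power statement in Section 15 concerns BMI change and does not bear on this point.

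**Set-up.** Let E = evening brush time minus reported last eating time, and M = morning brush time minus reported first eating time. The toothbrush window minus the survey window is then E - M. If E and M are independent, Var(E - M) = Var(E) + Var(M). Limits of agreement are mean ± 1.96 SD.

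**Inputs.**
- TRE evening lag: 0 to 0.5 h, from Sections 4.1 and 8.3. Taking it as uniform, with no eating afterwards, represents full compliance.
- Morning gap: not in the documents. Assumed uniform over ±0.5 h or ±1 h, centred on zero.
- SOC evening lag: not in the documents. Assumed uniform over 0 to 1.5 h or 0 to 3 h.

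**1. TRE, evening end only.** Mean 0.25 h; SD = 0.5/√12 = 0.144 h. Limits: 0.25 ± 0.283 = -0.03 to 0.53 h.

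**2. TRE, whole window.**
- Morning ±0.5 h: variance = 0.0208 + 0.0833 = 0.1042; SD 0.323 h. Limits: 0.25 ± 0.633 = -0.38 to 0.88 h. The morning supplies 0.0833/0.1042 = 80% of the variance.
- Morning ±1 h: variance = 0.0208 + 0.3333 = 0.3542; SD 0.595 h. Limits: 0.25 ± 1.166 = -0.92 to 1.42 h. The morning supplies 94%.

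The width rises from about 0.6 h to about 1.3 or 2.3 h with no change in evening behaviour. For assumed morning-gap SDs of 0.25, 0.5, 1.0 and 1.5 h, the half-widths are 0.57, 1.02, 1.98 and 2.95 h, and the morning share of variance is 75% to 99%.

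**3. Both arms pooled equally, if that were done.** The pooled variance is the average of the two arm variances plus (half the difference in arm means)².
- Morning ±0.5 h, SOC lag 0 to 1.5 h: (0.1042 + 0.2708)/2 + 0.25² = 0.25; SD 0.5 h; mean 0.5 h. Limits: -0.48 to 1.48 h.
- Morning ±1 h, SOC lag 0 to 3 h: (0.3542 + 1.0833)/2 + 0.625² = 1.109; SD 1.053 h; mean 0.875 h. Limits: -1.19 to 2.94 h.

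**4. Cancellation.** Suppose a child brushes one hour before first eating (M = -1) and snacks one hour after the evening brush (E = -1). Then E - M = 0. The windows agree perfectly although the evening cue failed.

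**5. Paired days available.** Each person has at most 5 × 3 = 15 log days under the Schedule of Events. TRE has 10 dyads × 2 = 20 people, so at most 300 person-days. Both arms together give at most 600.

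**The case against.** The strongest reply is that Section 3.1 itself speaks of brushing times, in the plural, and of the eating window. Section 4.1 says the toothbrush is there to approximate that window. A window comparison in TRE therefore does address the hypothesis. If morning brushing does not track the first meal, poor agreement is a true and useful finding. This stands. A reader might infer that the planned analysis cannot test its hypothesis, but the documents do not support that, and it is why the whole-window comparison should be kept.

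A reader might also infer that the plan pools the arms. Section 15 does not say so. It is silent, and it can be read together with the TRE restriction in Section 3.1. Supplying toothbrushes and logs to all families makes pooling possible but does not state it.

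Nor do the documents support the inference that the marker could be failed or discarded on this analysis. They set no threshold, pass/fail rule or go/no-go decision for it.

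Finally, the survey records both ends separately, so the data allow disagreement to be located. The gap is that Section 15 does not commit to doing so.

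**Conclusion.** The point holds as a mismatch between hypothesis and analysis, and as a missed chance to locate disagreement. As written, Section 15 does not restrict the comparison to TRE, may bring in SOC brushing that has no timing instruction, and combines an anchored with an unanchored time.

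The sizes are illustrative. The evening-only limits restate full compliance with the 30-minute instruction under a uniform lag. The whole-window and pooled limits rest on assumed morning and SOC gaps and on independence of the two ends. The direction is less fragile: any independent morning variation widens the whole-window limits without any change in evening behaviour. If the two gaps are positively correlated, cancellation operates instead. This is a low-cost improvement to a descriptive analysis in a 20-family pilot.

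**What to change.** In Section 15:

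- Make TRE the analysis set for the agreement hypothesis.
- Report agreement separately for evening brush versus same-day last eating time (main measure) and morning brush versus first eating time. Keep the whole-window comparison alongside.
- Show parent and child separately, with person nested within family in the mixed model.
- Report SOC descriptively.

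The change is to the analysis text and uses times the plan already intends to collect. The cost is slightly more analysis work and fewer paired days than with both arms: at most 300 rather than 600 person-days. These are ceilings. Dropout will lower them, as may the manual transfer of brushing data described in Section 16.8 ("The app for the toothbrush does not allow for sharing").

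### The GEE tests name no small-sample variance correction or reference distribution for 20 families; an uncorrected sandwich with z runs at 7.9–9.5% instead of 5%

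*Combined protocol and SAP*

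**What the plan says.** The Analysis Plan in section 15.0 states: "The primary outcome analysis will use a linear GEE model, with independence working correlation for family units". The outcome is the 12-week pre-post change in BMI, compared between TRE and standard of care. The plan adds: "This model will allow for estimating the TRE effect for children and adults while accounting for the correlation between parent and child measures". If the child/adult difference in effect has p ≥ 0.1, "the treatment assignment by child indicator interaction will be removed from the model". The method then extends to other outcomes: "A similar approach will be used to compare changes in measures of diet quality (average caloric intake and HEI"), and also eating and feeding behaviors, appetite and quality of life.

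The Sample Size paragraph gives the basis for power: "With n=20 per group (10 child-parent pairs), correlation between child-parent pairs ranging from 0.1 to 0.8, and an alpha= 0.05 significance level", and concludes that "we will have 80% power to detect a difference in BMI change (pre-post) between treatment groups of 0.96 to 1.25 standard deviations".

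Section 3.1 gives the number of clusters, "for a total of 10 families in each intervention group (N=20"), "with a retention rate of 70-80% across both groups".

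The only implementation detail is that R or SAS 9.4 will be used. No variance estimator, small-sample correction, reference distribution or degrees of freedom is given. The planned check of distributions, with transformation if needed, does not bear on the number of clusters.

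**The concern.** An independence working correlation treats parent and child as unrelated when the coefficients are estimated. Any allowance for their correlation must therefore come from the sandwich variance. That estimator is built from fitted residuals, which are too small on average, and the shortfall matters when there are only 7 to 10 families per arm. A normal reference then adds a second error, because it ignores the uncertainty in the estimated variance.

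Three results are at stake: the stated alpha of 0.05 for BMI change and the other GEE outcomes; the confidence interval for the treatment effect that the pilot will carry into a funding application; and the interaction step, which decides whether one pooled effect or separate child and adult effects are reported.

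**Working it through.** **Inputs.** From section 15.0: 10 dyads per arm, alpha 0.05 (taken as two-sided; the plan does not say), parent-child correlation ρ from 0.1 to 0.8, 80% power. From section 3.1: 70–80% retention, so 20 × 0.7 = 14 to 20 × 0.8 = 16 families, or 7–8 per arm if losses are equal. Assumed: normal data, and families lost as whole dyads.

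**The plan's own figure.** The difference in dyad means has SE = SD × √((1+ρ)/10). The effect detectable with 80% power is:

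| Reference | ρ = 0.1 | ρ = 0.8 | Power at 0.96 / 1.25 |
|---|---|---|---|
| Normal | 0.93 | 1.19 | 82.5% / 83.8% |
| t, 38 df (individuals) | 0.95 | 1.22 | 80.5% / 81.9% |
| t, 18 df (dyads) | 0.98 | 1.26 | 78.2% / 79.6% |

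The stated 0.96–1.25 is reproduced to within 2 points of power by either t version, but not by the normal version.

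**Size of the test.** With n complete dyads per arm, the independence-GEE treatment effect is the difference in mean dyad change. Its uncorrected sandwich variance is (n−1)/n times the unbiased variance. The unbiased statistic follows t on 2n−2 df, so:

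- size with z = 2·P(t₂ₙ₋₂ > 1.96·√((n−1)/n))
- size with t only = 2·P(t₂ₙ₋₂ > t₀.₉₇₅·√((n−1)/n))
- size with corrected variance and z = 2·P(t₂ₙ₋₂ > 1.96)
- CI width ratio (uncorrected, z) = 1.96·√((n−1)/n) / t₀.₉₇₅
- interaction size at nominal 10% = 2·P(t₂ₙ₋₂ > 1.645·√((n−1)/n)), because the interaction is the between-arm difference in the within-dyad contrast

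| | n = 10 | n = 8 | n = 7 |
|---|---|---|---|
| df | 18 | 14 | 12 |
| 1.96·√((n−1)/n) | 1.859 | 1.833 | 1.815 |
| t₀.₉₇₅ | 2.101 | 2.145 | 2.179 |
| Size, uncorrected with z | 7.9% | 8.8% | 9.5% |
| Size, uncorrected with t | 6.2% | 6.5% | 6.7% |
| Size, corrected variance with z | 6.6% | 7.0% | 7.4% |
| Size, corrected variance with t | 5.0% | 5.0% | 5.0% |
| CI width ratio, uncorrected with z | 88.5% | 85.5% | 83.3% |
| Interaction at nominal 10%, uncorrected with z | 13.6% | 14.6% | 15.4% |

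**Simulation.** Fitting the full GEE with a child indicator, with and without the interaction (40,000 runs per setting), agrees with these values. They barely change with ρ (0.1 or 0.8) or with unequal child and adult SDs. The separate adult and child effects behave the same way: about 8% at 10 per arm and 9.3–9.8% at 7 per arm.

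**Unequal losses** (simulated):

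| Families per arm | Uncorrected with z | Kauermann-Carroll, t on families − 2 |
|---|---|---|
| 7 v 9 | about 9% | 5.1–5.2% |
| 6 v 10 | about 9.5% | about 5.4% |
| 6 v 8 | about 9.7% | 5.1–5.2% |
| 5 v 9 | 10.6–10.7% | about 5.7% |

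With Satterthwaite df in place of families − 2, the corrected test runs at 4.8–4.9% in these cases.

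**Detectable effect on families − 2 df** (ρ 0.1 to 0.8): 0.98–1.26 SD with 10 dyads per arm, 1.12–1.43 with 8, 1.21–1.55 with 7.

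**The case against.** The strongest reply is that 7.9–9.5% rests on an implementation the plan never states. It neither names nor rules out an uncorrected sandwich with z, and its own power figure fits a t reference better than a normal one. On a dyad-level t without variance correction the excess is only 1.2–1.7 points. This stands as a limit on the size of the problem, but it does not remove it: every route that omits either correction exceeds 5%, and the power calculation does not bind the analysis.

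The second reply is that this is a pilot. Feasibility and acceptability are the primary endpoint in section 3.1, weight/BMI is secondary and expected to be comparable between groups, and no go/no-go rule depends on a BMI p-value. Wrongly keeping the interaction only means reporting separate child and adult effects, which are still unbiased. All of this is fair and lowers the stakes. Even so, section 15.0 calls this GEE the primary outcome analysis and sets an alpha and power for it, so the test should hold its level and the interval its coverage.

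Two narrower points also stand. Most of the rise in detectable effect to 1.12–1.55 SD comes from attrition; the small-sample step alone moves 0.96 to 0.98 and 1.25 to 1.26. And the sizes shown are for linear models; the logistic models planned for binary data were not checked.

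**Conclusion.** The concern holds. The plan leaves the variance estimator and reference distribution open for 20 families or fewer. With an uncorrected sandwich and z, chance differences would be declared 1.6 times (0.079/0.05) to 1.9 times (0.095/0.05) as often as stated, and 95% intervals would be 12–17% too narrow. After the anticipated attrition the size range is 8.8–9.5% with equal arms, and up to about 10.7% in the unequal splits examined. The interaction would be kept by chance in about 14–15% of trials rather than 10%.

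These figures assume normal data, two-sided tests and whole-dyad loss. The weight-trajectory mixed models, the parent-child correlation, the session-time and retention comparisons, and the SD and correlation estimates for planning the next trial are not affected. This should be corrected before analysis, but it does not undermine the pilot's main purpose.

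**What to change.** Keep the GEE. Add one sentence to the Analysis Plan: all linear GEE tests and confidence intervals, including the treatment-by-child interaction test, will use a bias-corrected sandwich variance (for example Kauermann-Carroll) with a t reference on (families − 2) degrees of freedom. Satterthwaite degrees of freedom can be named for the case where the arms end up unequal. With equal arms and complete dyads the pooled comparison is then the same as a two-sample t-test on dyad means. State separately what will be done for any binary outcome.

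Add one sentence to the Sample Size paragraph restating the detectable effect on the same basis: 0.98–1.26 SD with 10 dyads per arm, and 1.12–1.43 or 1.21–1.55 SD if 8 or 7 per arm remain.

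No new data or design change is needed. The price is intervals about 13–20% wider than the uncorrected z intervals (1/0.885 = 1.13; 1/0.833 = 1.20) and a slightly less favorable detectable effect before attrition.
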